4.1 Inclusion criteria

Adult (18 years and older) ED patients with all of the following (all determined pre-randomization):

1. VESTIBULAR SYMPTOMS: presenting symptom of “vertigo” OR “dizziness” OR “unsteadiness” (as defined by consensus expert definitions in the International Classification of Vestibular Disorders²⁵)
2. RELEVANT EXAM SIGNS*: pathologic nystagmus (spontaneous, gaze-evoked, or positional) by bedside VOG testing OR pathologic ataxia (gait, trunk, stance, limbs) by bedside ataxia examination
3. RECENT ONSET: symptoms AND signs* appear to be new or markedly worse in the past month

* Exam signs are required for randomization, but not for the observational arm

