4.2 Exclusion criteria

(Frequency and reasons for exclusion will be compiled and examined to plan for a follow-on Phase III trial)

Excluded from Pre-Randomization Screening

- Level 1 trauma or critical illness
- Altered mental status (e.g., delirium, dementia) that would preclude active study participation (this includes patients with abnormal mental state due to alcohol intoxication or illicit substance, which are known, easily-recognized causes of dizziness or vertigo presentations to the ED)
- Non-English speaking (enrollment of non-English speakers is not feasible given the logistics of identifying a translator and the need for rapid recruitment and randomization in the AVERT study; furthermore, the terms vertigo, dizziness, and unsteadiness may have different meanings in other languages¹⁵)
- Known pregnancy (all women of childbearing age who are enrolled will undergo a urine or serum beta-HCG pregnancy test prior to MRI to confirm no pregnancy, per local institutional guidelines)
- Unable or unsafe to participate in screening, including VOG tests (as deemed by specific pre-enrollment risk assessment questions or ED provider and/or Study Coordinator judgment) including, but not limited to:
 - visual impairment sufficient to prevent visual fixation during the VOG testing
 - clinically-perceived risk to patient of participating in study (ED provider or staff concerns)
 - clinically-perceived risk to research staff (e.g., violence, blood/body fluid/respiratory precautions)
 - unstable cardiac status (given a single reported case of bradycardia with impulse testing⁶¹)
 - acute cranio-cervical trauma or other condition (e.g., rheumatoid arthritis) that might lead to instability of the cervical spine that would be a contraindication to neck rotation during VOG testing
- Obvious general medical cause (as judged by treating ED provider) including, but not limited to, acute myocardial infarction, pulmonary embolus, pneumonia, urinary tract infection, drug intoxication, etc.

Excluded from Randomization (Eligible for Observational Arm Follow-up)

- Patient previously randomized in the AVERT Trial (*previously screened but not randomized are eligible*)
- Unable to participate fully with study follow-up (particularly MRI) including, but not limited to:
 - unable to return for follow-up testing within 30 days

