determining final diagnoses. The tests will include a vestibular exam by a neuro-otologist, repeat VOG, caloric testing, formal audiology, and MRI as applicable. The timing of the Week-1 visit will be determined based on optimal MRI sensitivity for detecting stroke and logistical constraints. The optimal MRI timing window for diffusion-weighted images to detect stroke is roughly 3-7 days after the onset of continuous dizziness or vertigo symptoms, although MRI-DWI detects acute stroke with high sensitivity out to 14 days or longer. We will define “T0” (time zero) as the time when dizziness symptoms began or most recently worsened, leading to the ED index visit. We will define “T1” as the ED registration time at the ED index visit. Follow-up MRI should not occur prior to 72 hours after ‘T0’ to reduce the odds of a false negative follow-up MRI scan for those with stroke. The target window for MRI is 3-7 days after T0, but up to 14 days will be considered acceptable for the purposes of inclusion in the primary outcome analysis (see Statistical Analysis Plan below). If T0 is unknown or uncertain, we will use time from T1 to determine the appropriate follow-up window. For scheduling purposes, the 1-week follow-up testing may be performed over two half days, separated in time. Regardless of exact timing, this visit will be known as the “1-Week” or “Week-1” follow-up visit.

6.2.4 30-Day Phone Follow-up: All subjects will complete a phone interview 30 days (+/- 7 days) after the ED Index Visit. In the event that no 6-month follow-up is possible (e.g., due to funds limitations), the subject will be instructed that this is the final visit. 30-day phone follow-up (~20-30 min) will repeat symptom and quality-of-life measures (see Schedule of Evaluations) and determine hospitalizations or doctor visits for stroke-related diagnoses (e.g., stroke, aneurysm, heart attack). We will review relevant medical records for vascular events, outpatient visits (particularly neurology or otolaryngology), ED visits, hospitalizations, and neuroimaging. Regardless of exact timing, this visit will be known as the “30-Day” or “1-Month” follow-up visit.

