The rationale for obtaining the delayed gold-standard MRI is that the sensitivity of MRI for detecting stroke is much greater at days 3-7 than in the first 72 hours after onset of symptoms. MRI sensitivity (using diffusion-weighted imaging [DWI] optimized for stroke detection) rises sharply in the first few hours after the onset of stroke symptoms. False negative scans are more frequent in the first 24 hours after onset of posterior fossa stroke symptoms than in the subsequent period from 24-72 hours after onset. MRI sensitivity is about 80%²⁹ <24 hours and about 86%⁷³ <72 hours. Maximal MRI sensitivity (~99%⁷³) is achieved after about 72 hours, and is maintained at a high level until ~14 days after onset of symptoms, then declines to a nadir around 1 month.¹⁰⁷ Accordingly, only those whose gold-standard MRI scans were obtained within the 14-day period will be included as part of the primary analysis for the main trial outcome (see Statistical Analysis Plan below).

Oral anxiolytic therapy may be offered to subjects per local institutional policy who have MRI anxiety. This will be documented in the subject's record and same-day follow-up assessments that may be affected by anxiolysis (e.g., vestibular testing) must be completed prior to anxiolytic administration.

MRIs will be read by two independent, masked study neuro-radiologists. For safety, all 1-week study MRIs will also be read clinically as an urgent ED scan by on-site clinical radiologists.

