Analytic approach: For all primary and linked secondary analyses, we will include only randomized subjects completing the essential elements of the diagnostic study protocol through the end of 1-week follow-up (i.e., with ED index visit VOG test results, follow-up MRI within 14 days, and an in-person neuro-otology visit within 30 days of the index visit). The quality of VOG and MRI testing will be determined by masked, expert raters from the FDAC during an FDAC meeting pre-review process; if either essential test is deemed to be of insufficient quality for analysis (e.g., key VOG tests performed improperly or missing; motion artifact on MRI), such patients will be excluded from the primary and linked secondary analyses of the main trial outcomes. This per-protocol analysis is appropriate for this Phase II study designed to determine the potential efficacy of the VRT intervention on diagnostic accuracy. Without adequate quality VOG and 1-week follow-up data, diagnoses will remain speculative. Subjects lost to follow-up at the 30-day time point (phone follow-up) will be included in these analyses, as 1-month medical record review will generally be sufficient to determine correct diagnoses.

Definitions: For the purposes of all analyses, the term “stroke” refers to any acute cerebrovascular event (ischemic stroke, transient ischemic attack, intracranial hemorrhage), unless expressly specified otherwise.

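### Entry allows symptom onset up to a month before the ED visit, but the primary analysis needs an MRI within 14 days of onset or last worsening, so some eligible patients can never be evaluable

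*Protocol*

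**What the plan says.** Entry. Criterion 3 of Protocol 4.1 asks that "symptoms AND signs* appear to be new or markedly worse in the past month", determined before randomisation. Among the exclusions from randomisation in Protocol 4.2, the explicit timing item is "unable to return for follow-up testing within 30 days". It sits under a broader, open-ended criterion on inability to complete follow-up, which singles out MRI.

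The MRI clock. Protocol 6.2.3 defines T0 "as the time when dizziness symptoms began or most recently worsened, leading to the ED index visit". It then says: "The target window for MRI is 3-7 days after T0, but up to 14 days will be considered acceptable" for the primary outcome analysis. There is a fallback: "If T0 is unknown or uncertain, we will use time from T1 to determine the appropriate follow-up window", where T1 is ED registration. The research scan is not to be done before 72 hours after T0.

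The consequence. Protocol 6.3.18 explains that MRI sensitivity for stroke stays high until about 14 days after onset and then falls to its lowest point at around one month. Accordingly, "only those whose gold-standard MRI scans were obtained within the 14-day period will be included as part of the primary analysis".

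The analysis set. Protocol 9.1 (Analytic approach) is per-protocol and requires "follow-up MRI within 14 days, and an in-person neuro-otology visit within 30 days of the index visit". It does not restate where the 14 days start. SAP 2.2.1 defines the primary population by the presence of a 30-day adjudicated final diagnosis and gives no MRI window.

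**The concern.** The entry window for onset (about 30 days) is roughly twice the window in which the reference scan counts (14 days), and both concern the same event. No explicit entry rule compares the two. A site that follows the criteria as written can randomise a patient whose qualifying MRI date has already passed. That patient goes through trial procedures and takes a place among the 226 but is removed from the primary outcome by rule. T0 is normally known at screening, so this loss is avoidable, and the sample size makes no provision for it.

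**Working it through.** Step 1: compare the windows. Let k be the number of days from T0 to the ED visit, with T0 known and no later worsening. Days left after the visit for a qualifying scan = 14 - k.

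- k = 15 to 30: 14 - k is negative. The patient meets criterion 3, but the window closed before randomisation and no scan date can qualify.
- k = 10: 14 - 10 = 4. A scan on days 1 to 4 after the visit counts.
- k = 0, but the patient can return only on days 15 to 30: the 30-day item is passed and the MRI window is missed. The result is the same if the fallback clock T1 applies.

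Step 2: reproduce the planned sample size. Protocol 9.3 and SAP 2.3 (Table 3) give 113 per arm for 90% vs 75%, alpha 0.05, power 80%. With d = 0.15 and mean proportion 0.825:

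- Uncorrected, two-sided: n' = [1.960 x sqrt(2 x 0.825 x 0.175) + 0.842 x sqrt(0.90 x 0.10 + 0.75 x 0.25)]^2 / 0.15^2 = 99.5, so 100.
- Continuity-corrected: n = (n'/4) x [1 + sqrt(1 + 4/(n' x d))]^2 = 112.5, so 113.

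The corrected two-sided formula returns all six rows of Table 3 (15, 19, 25, 38, 59, 113). The number to be randomised is 226 = 2 x 113, so the allowance for non-evaluable patients is zero.

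Step 3: effect of a loss q. The documents give no distribution of onset times; the symptom-onset bands in Protocol 9.2.1 stop at more than 72 hours. The share q is therefore an assumption, shown as a range. Evaluable n per arm = 113 x (1 - q). Uncorrected power = Phi{[d x sqrt(n) - 1.960 x sqrt(0.28875)] / sqrt(0.2775)}. For corrected power, replace n by n x [1 - 1/(d x n)]^2. The last column is 113/(1 - q), rounded up.

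| Assumed loss q | Evaluable per arm | Power, corrected | Power, uncorrected | Randomise per arm (total) to keep 113 |
|---|---|---|---|---|
| 0% | 113 | 80.2% | 84.8% | 113 (226) |
| 5% | 107 | 77.9% | 82.9% | 119 (238) |
| 10% | 102 | 75.3% | 80.8% | 126 (252) |
| 20% | 90 | 69.4% | 76.1% | 142 (284) |

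Protocol 9.2.1 plans a score test equivalent to the Pearson chi-square, so the uncorrected column is closer to the planned analysis (before any allowance for clustering). On that column, power stays at about 80% until the loss reaches about 11.5%, since 113 x 0.885 = 100 per arm gives 80.2%.

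**The case against.** Several points narrow the concern, and most of them stand.

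- A reader might infer that, with the follow-up visit at one week plus or minus 3 days, anyone with onset more than 4 to 10 days before the ED visit is lost. The documents do not support this. The footnote to Protocol 6.1 and the text of 6.2.3 time the scan from symptom onset, and 6.2.3 lets testing be split over two half days. Onset up to 14 days before the visit is a scheduling matter.
- T0 is not simply first onset. It includes the most recent worsening, and T1 takes over when T0 is unknown or uncertain. Many patients with month-old symptoms may therefore still qualify. Only a known T0 more than 14 days before the visit is impossible from the start.
- The parent exclusion in Protocol 4.2 names MRI and is not exhaustive, so a site may already use it to exclude such a patient. That is discretion, though. It mentions neither T0 nor 14 days.
- A reader might infer that Protocol 9.1 sets a second, conflicting clock from the index visit. Under it, a patient with T0 20 days before the visit and scanned 7 days after it would count, with a reference scan 27 days after onset. The reference to the index visit attaches most naturally to the neuro-otology visit, and 6.2.3 and 6.3.18 both count the MRI window from T0 or onset. This is a gap in wording rather than a demonstrated conflict.
- The 30-day return item is not an error. It matches the neuro-otology window in 9.1 and is too loose only for the MRI.
- The plan calls 90% vs 75% a worst case, and with the planned uncorrected test a modest loss still leaves 80% power.

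What remains is the group with a known early T0, and those who can return only after the MRI window. No explicit rule stops either from being randomised.

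**Conclusion.** The point holds for a defined group. Patients with a known T0 more than 14 days before the ED visit meet the recent-onset criterion yet cannot enter the primary analysis, and patients who can return only after T0 + 14 days pass the stated 30-day item and are lost as well. This rests on the protocol's T0 rule being in force. The SAP's primary population, read alone, carries no MRI window, so the two documents should be aligned.

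The size is unknown. Over an assumed 5% to 20% loss, power falls to about 78% to 69% by the corrected formula, or 83% to 76% for the planned test.

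A reader might also infer that the exclusions bias the comparison. For exclusion on T0 alone they do not: T0 is fixed before randomisation, so the cost is precision and wasted enrolment.

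**What to change.** - Keep the 30-day return item for the neuro-otology visit. Under the same parent criterion in Protocol 4.2, add an item such as: research MRI not feasible between 72 hours and 14 days after T0 (T1 if T0 is unknown or uncertain).
- Have the EDC compute T0 + 14 days at screening from the onset data already collected. Do not require a booked scan slot, because Protocol 6.2.2 randomises immediately after eligibility screening.
- Send those who fail the check to the existing observational arm.
- State the same T0/T1 clock in Protocol 9.1 and in the SAP's definition of the primary analysis set.

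The cost is protocol and SAP wording plus a date check in the EDC. Slightly fewer patients will be eligible for randomisation, but under the T0 clock none of them could have counted in the primary analysis. With the check in place, 226 needs no increase on this account; losses for other reasons are a separate matter.

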4.2 Exclusion criteria

(Frequency and reasons for exclusion will be compiled and examined to plan for a follow-on Phase III trial)

Excluded from Pre-Randomization Screening

- Level 1 trauma or critical illness
- Altered mental status (e.g., delirium, dementia) that would preclude active study participation (this includes patients with abnormal mental state due to alcohol intoxication or illicit substance, which are known, easily-recognized causes of dizziness or vertigo presentations to the ED)
- Non-English speaking (enrollment of non-English speakers is not feasible given the logistics of identifying a translator and the need for rapid recruitment and randomization in the AVERT study; furthermore, the terms vertigo, dizziness, and unsteadiness may have different meanings in other languages¹⁵)
- Known pregnancy (all women of childbearing age who are enrolled will undergo a urine or serum beta-HCG pregnancy test prior to MRI to confirm no pregnancy, per local institutional guidelines)
- Unable or unsafe to participate in screening, including VOG tests (as deemed by specific pre-enrollment risk assessment questions or ED provider and/or Study Coordinator judgment) including, but not limited to:
 - visual impairment sufficient to prevent visual fixation during the VOG testing
 - clinically-perceived risk to patient of participating in study (ED provider or staff concerns)
 - clinically-perceived risk to research staff (e.g., violence, blood/body fluid/respiratory precautions)
 - unstable cardiac status (given a single reported case of bradycardia with impulse testing⁶¹)
 - acute cranio-cervical trauma or other condition (e.g., rheumatoid arthritis) that might lead to instability of the cervical spine that would be a contraindication to neck rotation during VOG testing
- Obvious general medical cause (as judged by treating ED provider) including, but not limited to, acute myocardial infarction, pulmonary embolus, pneumonia, urinary tract infection, drug intoxication, etc.

Excluded from Randomization (Eligible for Observational Arm Follow-up)

- Patient previously randomized in the AVERT Trial (*previously screened but not randomized are eligible*)
- Unable to participate fully with study follow-up (particularly MRI) including, but not limited to:
 - unable to return for follow-up testing within 30 days
 - unable to undergo MRI because of contraindications (e.g., pacemaker, metallic foreign body, pregnancy) or other reasons (severe claustrophobia, too large or too heavy for MRI scanner)

4.3 Study enrollment procedures

4.3.1 Sampling: Consecutive during shifts. Recruitment shifts will be Monday to Friday during peak hours (window between 8AM–7PM). Total ~35 hours per week.

4.3.2 Identification & Recruitment: A full-time study coordinator (SC) at each site will screen, recruit, and collect clinical data. The SC will be stationed in the hospital to systematically identify potential subjects and maximize early recruitment, using both active and passive (notified by ED staff) surveillance. We will actively pre-screen chief complaints under a HIPAA waiver, and approach potentially eligible patients for pre-screening and consent. After granting consent, patients will undergo VOG testing to determine trial eligibility.

4.3.3 Documentation for Ineligibility: Patients with a chief presenting symptom of vertigo, dizziness, or unsteadiness, whether eligible or not, who have been screened by study personnel at participating hospitals will be documented in the VISION Electronic Data Capture (EDC) system. All reasons for exclusion for each

patient not entered into the trial will be recorded. Each participating hospital will enter screening data into the VISION EDC system using a standardized electronic data capture procedure (see ‘Digivey’ below). Subjects completing the screening procedure will be identified as ineligible (a pre-screen or screen failure) or will be randomized. Monthly reports of subject accrual (pre-screened, screened, randomized) and other protocol compliance data will be maintained by the CC and monitored for site performance.

4.3.4 Logistical Pilot Subject Recruitment for Training: During the trial start-up period, each site was approved to obtain consent from up to approximately 250 subjects to collect preliminary data in order to test the data collection procedures and logistics. For the logistical pilot trial, enrollment occurs at the time of consent. These subjects who consented also served to test the VRT algorithm, and as training for site personnel in the administration of the VOG test and additional clinical exams. Consent was obtained from pilot subjects for participation, including 1-week and 30-day clinical follow-up. A sample pilot study consent document is found in v3.2 of the AVERT protocol document, but has been removed from the main trial protocol (v4.0). The consent procedure for these pilot study subjects differs from the full study participants, and the consent form and procedure identified the specific aspects of the study in which the patients were participating (which varies during the pilot period). The rationale for having a flexible pilot protocol was twofold: (1) *staged beta testing of data collection instruments and procedures* – for the initial patients we did a very limited data collection to test the consent procedures, electronic data capture forms and data transfers; subsequent patients went through the full 1-month data collection protocol, including follow-up; the final group of patients will complete the entire protocol, including randomization to VOG care; (2) *availability of funds for follow-up testing* – we sought to test the procedures for scheduling and conducting these exams at each site, but did not have sufficient funds for all pilot participants to complete the full protocol with follow-up advanced testing (MRI, vestibular lab tests).

4.3.5 Consent/Ethics: Patients will be offered enrollment using a standard written consent procedure. A sample AVERT (main) trial consent is provided in the Appendix. For the main trial, consent will be obtained during screening with enrollment into the trial occurring at the time of randomization. The testing involves minimal risk, identical to that in routine specialty care (neuro-otologic exam). Randomization is ethical because we are in research equipoise: (1) eye movement approaches to diagnosis are established⁶³; (2) the VOG device has proven measurement accuracy^{52,53,64,65}; but (3) the impact of VOG on clinical management and outcomes is uncertain. We will obtain VOG in all patients, then randomize to disclosure (VRT) or non-disclosure (standard care). The ethical nature of non-disclosure in diagnostic trials has been discussed in detail by Fost and Farrell.⁶⁶ The key reasons why such trials are considered ethical are that (1) patients are not being denied anything of known value, (2) disclosure may cause harm, and (3) subjects consented to the conditions of non-disclosure.⁶⁶ Trial risks and safety of head impulses (routine in specialty care) are summarized in Section 7 Risks.

Study personnel will obtain consent at two different time points for patients who are enrolled at St. Joseph Mercy Health System. The first consent will be obtained at the St. Joseph Mercy Health System for activities that take place at St. Joseph Mercy Health System. The second consent will be obtained at the time of the approximately 1-week follow-up visit at the University of Michigan for the University of Michigan activities. This is because the two sites operate under different IRB structures, despite their institutional affiliation.

4.3.6 Randomization: Patients who meet all of the inclusion and exclusion criteria using the above screening procedures and who provide consent will be randomized. AVERT randomization will initially assign each patient to a block size of 2 or 4, with a 50-50 probability; all site personnel will be masked to this block assignment. Then, when the patient is determined to be eligible for the study, the patient will be randomized using VISION’s randomization framework, stratified by site and block size, so that all patients assigned to size “2” are randomized in blocks of 2 and all patients assigned to “4” are randomized in blocks of 4 at each site. In this way, it would be difficult for the site personnel to predict the next assignment, as they will not know which patients are in which block.

VISION’s just-in-time randomization framework generates each random treatment at the moment a patient is randomized, instead of reading from a pre-computed table of treatments. This automatically compensates for

imbalances caused if a previously-randomized patient drops out of the study or accidentally receives the wrong treatment. When a random choice is made, VISION uses a cryptographically-strong SecureRandom random number generator. The SecureRandom algorithm computes the SHA-1 hash over a true-random seed value concatenated with a 64-bit counter, which is incremented by 1 for each operation. From the 160-bit SHA-1 output, only 64 bits are used. As a result, there is no known computer analysis which is able to predict the next “toss” better than 50% of the time.

4.3.7 Masking (blinding): Allocation will be known to SC, ED provider(s), and patients (VOG result added to the medical record in the intervention arm), in order to guide management in the ED. This allocation will also be known to a small number of personnel at the CC, including members of the biostatistics team. The Investigator will become unmasked to allocation status for patients who have completed their final diagnosis adjudication as part of the iterative VRT algorithm refinement process (see Section 5.1.1). Since this is a diagnostic (not therapeutic) trial, masking is most crucial for outcome assessors, who will adjudicate final diagnoses ‘offline,’ masked to allocation status. Procedures will be used to ensure maximal masking of the Final Diagnosis Adjudication Committee (FDAC) members to trial allocation. In particular, all testing protocols are the same between the two arms of the study other than the required “safety MRI” in the VRT arm (Figure 1). The risk of unmasking of allocation therefore relates to patients in the standard care arm who do *not* undergo clinical MRI. The FDAC process will proceed in two discrete stages separated in time: (1) based solely on ED index visit data *without* the safety MRI; (2) based on all clinical data through the 30-day follow-up. Study radiologists will be masked to the index visit scan purpose/type (“safety MRI” vs. “pathway MRI” vs. “clinical MRI”), so the presence or absence of an imaging study will not cue them to the allocation during the first stage of FDAC review. During the second stage of review, study radiologists will reference any prior imaging studies using standard language that prevents disclosure to the other FDAC members whether a prior imaging study was or was not available (e.g., “The present study was compared to any prior studies, if available, and revealed no evidence of interval change.”). The actual FDAC review will occur approximately 1 month after these images are interpreted, so the neuro-radiologist, when reviewing this summary, will generally not recall which subjects did or did not have MRI imaging prior to the definitive, 1-week research MRI. If they do recall this information for a particular subject, they are instructed not to indicate this to the remaining FDAC members.

